#### **B. Human Subjects Protection- Recruitment and Informed Consent**

Participants will be recruited through community hospitals, rehabilitations, and home health services. We will recruit from area speech language therapy service centers by placing advertisements in the waiting areas and asking professionals including neurologists, otolaryngologists, and speech-language pathologists to place notices in their waiting and office areas. Notices will also be mailed to professionals involved in rehabilitation in the Shenandoah Valley area asking them to place notices in their waiting and office areas. We will also be using email blasts, discussion board postings, and a website ([swallowselftrainer.com](http://swallowselftrainer.com)) to increase awareness of the study among speech language pathologists and patients with swallowing disorders in the community. We will only ask professionals to place notices and make literature available on our study but not to refer patients directly to us so patients will not feel under any undue influence from their professional caregivers to participate. Our notices and literature will provide information that will allow participants to contact us directly and the website will allow patients to self-refer.

We have 3 rooms in the JMU-SRMH Voice and Swallowing Service to support multiple participants being tested simultaneously. Free parking is immediately available within 100 ft of the entrance to our testing rooms in the Treatment Center on the ground floor of SRMH. The burden to participants will be the daily use of the Self-Trainer for 3 months, the majority of which the device will be switched in "automatic" mode requiring no active engagement on the part of the participant. Active practice required of the participant consists of 60 swallows and will take from 30-60 minutes a day. Additional burden to the participant includes 3 or more visits to SRMH for testing measures, while periodic counts taken from the Self-Trainer can be completed with laptops and can be done in the participant's home, JMU or SRMH as is convenient. Weekly check ins can be done over the telephone, Skype, or as needed by the participant to answer questions and verify compliancy, although in person appointments can be made if needed.

Administration of informed consent: Participants will be telephone screened and if they meet the inclusion criteria, they will be mailed the consent form for information purposes to allow them to review it before coming to the Voice and Swallowing Service. The consent will inform participants that [name] has a financial interest in the research. Either [name] or [name], the speech language pathologist, will administer informed consent to the participant. During the consent process, either [name] or [name] will review the study with the participant and any family members present to answer questions. The participant will then read or be read the consent and answer a few questions to demonstrate they have

understood. The consent will then be signed, witnessed, and a copy given to the participant. Participants who have sight or literacy problems will have the consent read to them and a series of questions will be asked of all participants to assure their comprehension of the study before completing the informed consent process. No proxy consent or assent will be accepted for this study.

**C. Protection against risk**

As listed above under Potential Risks, this application is expected to involve only minimal increased risk from the research procedures for participants with swallow disorders as only saliva swallows or 1-2 ml water swallows as needed (equivalent to a saliva swallow) will be used while the device is on. All participants will be producing saliva normally and will be exposed to the risk of saliva aspiration throughout the day in their normal living. This risk occurs even when they are receiving enteral feeding either through a PEG tube or nasogastric tube. With the increased frequency in swallowing associated with the Self-Trainer, there is a minimal increased risk for the participant because of their swallowing disorder.

To minimize the risk associated with saliva aspiration, the speech language pathologist conducting the research will train all participants and their caregivers on a daily regimen to follow for secretion aspiration prevention and an oral hygiene regime to reduce oral bacteria. Each participant and their caregivers will be trained to competency on the following aspiration monitoring methods:

1. Oral hygiene including cleaning the mouth, teeth (or dentures), tongue, etc. with toothpaste and mouthwash, as deemed appropriate, after meals or 3 times a day.
2. Voice quality testing to detect a wet, gurgly voice quality which would indicate increased fluid in or around the airway. If voice quality sounds “wet” they will be trained to voluntarily move secretions away from the airway by throat clearing/coughing to bring the secretions in the mouth and then spitting or swallowing the materials brought up.
3. Daily body temperature monitoring: The participant and their caregivers will be instructed to contact the research staff if they have a rise in body temperature over three days sequentially while participating in the study.
4. Participants and caregivers will be instructed to only use the Self-Trainer while sitting in an upright position, which may be helpful in preventing the aspiration of oral secretions. If the participant needs to lay down for any reason, the Self-Trainer should be switched off and/or removed from the participant’s neck. They will also be instructed not to use the self-trainer during vigorous exercise (like running) as this would be cumbersome and could result in damage to the device.
5. Participants will be instructed not to use the device with any oral intake they are unsafe for. The SLP will make recommendations as to what food consistencies the participant is safe for consuming while using the device. If they are unsafe on all consistencies, the recommendation will be not to wear the device while there is any food in their mouth.

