### Participant and Caregiver Instruction

Each participant and their caregivers will be trained in the following: 1) Self-Trainer placement; 2) Self-Trainer charging and use; 3) Self-Trainer cleaning; and 4) Aspiration precautions. Participants and caregivers will learn to locate the thyroid notch (Adam's apple) and place the motor contacts so that they are on either side of the thyroid notch (Figure 1). Each participant's device attachment cuff will be marked to illustrate where the Velcro should be secured to assure appropriate tightness for a neck pressure that is comfortable but effective for inducing swallowing during vibration. The participant and caregiver will also learn to verify correct placement by phonating while the vibration is on to determine if they can hear the sound of the vibration in their voice to indicate correct placement.

The participant and caregiver will learn the differences between automatic and manual modes and how to change the device to operate in each mode. Verbal, written, and/or video instructions will instruct the participant and caregiver to secure the Self-Trainer to the outside of the participant's neck (as described above) every morning after breakfast with the device set in automatic mode. The participant will wear the Self-Trainer set to automatic mode during waking hours with the exception of mealtimes, swallowing practice and during vigorous exercise when it may be cumbersome to use. The participant will learn to correctly sequence active swallowing practice with the Self-Trainer, which involves the following steps: 1) pushing the button to turn on the device vibration, 2) initiate swallowing within a 1/3 of a second while the vibrator is "on", and 3) releasing the button when the swallow is completed. Participants will be given written, pictorial, and/or video instructions on how to use the device and how to verify correct placement of the device. Instruction and training will be provided on how to daily clean and charge the device. Participants will learn to follow a daily regimen for preventing aspiration of secretions and for preventing aspiration pneumonia including good oral hygiene, monitoring for wet vocal quality, taking their body temperature, and only using the Self-Trainer in an upright position (see Human Subjects Protection).

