#### C. Training session

- a. The participants will be trained on appropriate device placement, appropriate device pressure, how to verify correct placement of the device, and how to use the device daily for swallowing therapy. Caregivers will be encouraged to attend to provide support and will be trained to "coach" the participant.
- b. Self-Trainer guides will be given to the participant in the following forms:
  - i. Written directions with pictures
  - ii. Optional DVD instructional video
- c. Once the participant and their caregiver can demonstrate correct use of the Passy Muir Self Trainer for Swallowing, they will be given the device to take home and use for 3 months. The investigators will provide phone support to the participant and caregivers every day for the first 3 days of participation and on a weekly basis after that. The participants and caregivers will be encouraged to call the investigators with questions as needed and the investigators will be available for one on one meetings as needed. All contacts will be documented.

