For participants who take food orally these consistencies must be approved by the SLP as being safe to use with the device. If the participant is not safe for any intake, instructions will be given to remove the device from the participant's neck prior to food consumption they take for pleasure. As the Self-Trainer is known to increase the frequency of swallowing, the participants will be swallowing their secretions more frequently and therefore it is possible that each participant's risk of aspirating could change. For some participants, specifically those who do not swallow their secretions and instead periodically expectorate, the participant is now attempting to swallow the secretions instead of attempting to clear them from their oropharynx using regurgitation. Participants who do not feel secretions pooling in their throat may have a decreased risk of aspirating secretions while using the device as they are now prompted to swallow. As saliva swallows and the risks associated with saliva aspiration are an ongoing daily risk for these participants, this study provides only a minimal increase in risk. Efforts will be made to minimize any risk associated with participation in this study (see Protection against risks). If a participant expectorates their saliva as a part of reducing aspiration risk, they will be encouraged to continue with this practice as needed, but to try to swallow when they feel the urge to swallow as part of the self-training. The study will be conducted by a licensed speech language pathologist who will counsel each participant on minimizing secretion aspiration risk.

Participants will be encouraged to continue with their current swallowing treatment plan of care as determined by their speech language pathologist. We will take great care to make certain that all participants and their family and caregivers do not misinterpret the purpose of this research and fully understand that this study is experimental research with no guarantees of benefit. It will be made clear in the advertising material, informed consent and in any discussions with the participants and family members that treatment received is experimental research and there is no guarantee of improvements in swallowing function. The speech language pathologist conducting the research will provide participants and their

caregivers with referrals to patient services in their area for treatment of their swallowing disorder if appropriate.

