**D. Adverse events**

Participants will be monitored for the occurrence of adverse events throughout their enrollment in the clinical study. All adverse events occurring during the course of the clinical study, whether device-related or otherwise, will be recorded on the Adverse Event CRF. Records of adverse events (AE) will be evaluated by the medical officer, [name], the Study Team and the JMU and SRMH IRBs for participants in the protocol. Serious adverse events (SAE) will be evaluated by [name] and reported to the IRBs at JMU and SRMH within 10 days of their occurrence. The study physician will assess and report on the relationship of the adverse event to the investigational device as well as the severity of the event, the outcome of the event, and whether or not the adverse event could have been anticipated. The IRBs will evaluate the reports of AEs/SAEs to determine if use of the device shows increased risk of aspiration pneumonia and other problems indicating that use of the device produces “more than minimal” risk.

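### The only bodily sign tied to contacting staff is a three-day temperature rise with no level, so a fever of any height need not be reported on its first two days

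*Protocol*

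**What the plan says.** The trigger is item 3 of the aspiration monitoring list in Protocol, Human Subjects Protection, C. Protection against risk. Participants and caregivers are "instructed to contact the research staff if they have a rise in body temperature over three days sequentially while participating in the study". No temperature level, size of rise or reference value is given.

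The other relevant text is:

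- **Participant and Caregiver Instruction** lists daily temperature-taking without a threshold. It points back to the same section: "only using the Self-Trainer in an upright position (see Human Subjects Protection").
- **C. Protection against risk, item 2 (wet voice):** "they will be trained to voluntarily move secretions away from the airway by throat clearing/coughing". It does not tell them to contact staff.
- **C. Training session, item c:** staff telephone "every day for the first 3 days of participation and on a weekly basis after that". Participants are also "encouraged to call the investigators with questions as needed".
- **Section B of Human Subjects Protection** describes the weekly check-ins, which may be held "as needed by the participant to answer questions and verify compliancy".
- **D. Adverse events** provides for monitoring throughout enrolment, and the IRBs review the reports "to determine if use of the device shows increased risk of aspiration pneumonia". It names no sign on which a participant must call.

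**The concern.** Temperature is the one home sign meant to bring staff in, and the rule attached to it waits three days and names no level. A participant who follows it exactly can have a high fever for two days while still using the device and have no stated duty to report it.

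All participants have oropharyngeal dysphagia. Section A. Potential Risks says that each participant's "risk of aspirating could change" with the device, and aspiration pneumonia is the named event of interest. What is at stake is prompt notice to staff of a possible aspiration event. The estimates are not at stake. The three-day condition is a rule that the protocol itself fixes, so it is not a detail left to another document.

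**Working it through.** The protocol gives no figure on this point, so there is none to reproduce. Steps 1 to 3 rest on the wording and the call schedule. Step 4 rests on assumed inputs and is illustrative only.

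**1. Ordinary reading: temperature raised on three consecutive days.** The condition cannot be complete before the third raised day. No call is due on fever days 1 and 2 at any height, and a fever of one or two days never requires a call. Because no level is stated, it is also unclear what counts as raised.

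**2. Literal reading: temperature rises day on day.** Take a jump from normal to fever that then stays level. The sequence is one rise followed by no change. Three rising readings need two rises, and three successive increases need three. Without measurement noise neither is reached, however long the fever lasts. A fever that climbs over several days would be caught. If the last normal day counts as the first reading, the rule could be met on the second fever day, but only if that day's reading is higher again.

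**3. Scheduled calls as a back-up.** Inputs: calls on days 1, 2 and 3, then weekly (Training session, item c), and 3 months of use taken as 90 days. The day of the first weekly call is not stated, so day 4 to day 10 is assumed. An onset day is covered if a call falls on it or on the next day.

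- First weekly call on day 5: the early calls cover onset days 1 to 3. Thirteen weekly calls (days 5, 12, ..., 89) cover 2 × 13 = 26 more. Uncovered: 90 − 3 − 26 = 61.
- First weekly call on day 8: twelve weekly calls (days 8, 15, ..., 85) cover 2 × 12 = 24. Uncovered: 90 − 3 − 24 = 63.
- First weekly call on day 4, 5, 6, 7, 8, 9 or 10: 62, 61, 61, 62, 63, 63 or 63 uncovered.

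So 61/90 = 68% to 63/90 = 70% of onset days have no scheduled call on fever day 1 or 2. Calls that participants choose to make are not counted.

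**4. Illustrations on assumed inputs.**

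*Three-day wait against a single reading at the same level.* Let p be the chance that a reading on a fever day meets the level, with days independent. The three-day rule has prompted a call by day 3 with probability p³. The single-reading rule has done so on day 1 with probability p, and by day 2 with probability 1 − (1 − p)².

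| p (assumed) | Three-day rule, by day 3 | Single reading, day 1 | Single reading, by day 2 |
|---|---|---|---|
| 0.80 | 51% | 80% | 96% |
| 0.90 | 73% | 90% | 99% |
| 0.95 | 86% | 95% | 99.8% |

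*No fever.* Assumptions: 90 daily readings around 36.8 °C, SD 0.15 to 0.30 °C, lag-1 correlation 0 to 0.6, rounded to 0.1 °C. At least one trigger by chance occurs in nearly all participants for three rising readings, in 59 to 97% for three successive increases, and in 96 to 100% for at least 0.1 °C above usual on three days running.

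*Abrupt fever level at 38.8 °C.* Assumptions: SD 0.2 to 0.3 °C, independent days. Three rising readings are met by fever day 2 in 43 to 46%, counting the last normal day as the first reading. Three successive increases are met by fever day 3 in 10 to 12%. Both depend on noise to complete the run.

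**The case against.** The strongest reply is that the absence of a duty to call is not an instruction to wait.

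- Nothing shown tells a participant with fever to delay a call or medical care. As-needed calls and one-to-one meetings are offered, and it would be strained to read an invitation to raise questions as excluding a report of fever.
- Participants continue their outpatient rehabilitation and their own clinician's plan, and adverse events are monitored throughout.
- The protocol describes the added risk as minimal and says that some participants may be at lower risk of aspirating with the device.
- Participants are trained to competency, and the guides and consent form, which could hold a cut-off, are not shown.
- The natural meaning of item 3 is a raised temperature that persists, so the drift figures test readings that a trained participant is less likely to use.

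Most of this stands and limits the point. The 68 to 70% describes scheduled calls only and is not the chance that a fever goes unaddressed. The simulations have no inputs from the protocol. But none of these provisions sets a temperature level, shortens the three days or ties a sign to a duty to call. If the guides are clearer, item 3 should match them.

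A reader might infer that the rule leaves adverse event records incomplete or biases the IRBs' judgement of pneumonia risk. The document does not support that: section D records all adverse events whatever prompts their discovery, and the rule governs only when a participant must call.

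**Conclusion.** The point holds as a weak safety instruction that is worth changing. It is not a threat to the validity of the case series.

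On the ordinary reading, no report is required on the first two days of a fever of any height. On the literal reading, a sudden level fever may not meet the rule at all. Both follow from the wording. The other contacts reduce the gap without closing it. The 61 to 63 of 90 onset days without a scheduled call rests on the stated schedule plus an assumed first weekly call between days 4 and 10. The simulated percentages show direction only.

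The conclusion is limited to the text shown. It does not extend to saying that participants are told to wait, that fevers would go untreated, or that any adverse event record or outcome estimate is affected.

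**What to change.** Add a same-day trigger to item 3 and keep the three-day clause for lower, persistent rises. Suggested wording: *contact the research staff the same day if any daily reading is at or above [cut-off set by the medical officer], or if temperature stays above the participant's usual level by [margin set by the medical officer] for three consecutive days.* Match the participant instructions, and leave adverse event recording in section D as it is. Keeping the second clause matters, because a cut-off alone would drop a persistent rise that stays below it.

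The margin must be clear of ordinary variation: in the illustration above, 0.1 °C would be met by chance in almost every participant. The participant's usual level also has to be noted, which the readings already taken can supply.

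Cost: one reworded item and the matching instruction. Temperature is already taken daily, so no visit is added. Readings number 12 × 90 = 1,080 to 20 × 90 = 1,800. If 1 in 10,000 to 1 in 500 fever-free readings reaches the cut-off (assumed), the same-day clause adds 1,080 × 0.0001 = 0.1 to 1,800 × 0.002 = 3.6 unneeded calls in the whole study. Calls from the three-day clause depend on the margin chosen.

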**D. Adverse events**

Participants will be monitored for the occurrence of adverse events throughout their enrollment in the clinical study. All adverse events occurring during the course of the clinical study, whether device-related or otherwise, will be recorded on the Adverse Event CRF. Records of adverse events (AE) will be evaluated by the medical officer, [name], the Study Team and the JMU and SRMH IRBs for participants in the protocol. Serious adverse events (SAE) will be evaluated by [name] and reported to the IRBs at JMU and SRMH within 10 days of their occurrence. The study physician will assess and report on the relationship of the adverse event to the investigational device as well as the severity of the event, the outcome of the event, and whether or not the adverse event could have been anticipated. The IRBs will evaluate the reports of AEs/SAEs to determine if use of the device shows increased risk of aspiration pneumonia and other problems indicating that use of the device produces “more than minimal” risk.

## **Data Analysis**

Data integrity will be assured by using the LabTrack electronic notebook system in [name] lab which is on a secure backup server. This system meets FDA standards for data monitoring. Case Report Forms (CRF) will be setup with templates requiring entry of all essential data elements on each participant such as inclusion/exclusion criteria, consent records and records of visits, telephone contacts, and correspondence tracking each participant's involvement in the research. The LabTrack system tracks all entries, the date and the identity and any data changes by user ID. All measures will be entered into data files on the Laboratory server by participant ID number. All videos associated with the study will be stored on encrypted drives for at least 5 years. The PI and speech pathologist will conduct monthly quality assurance reviews of the CRFs and data files.

The outcome measure data points will include training and maintenance data, participant feedback survey, fidelity data, MBSImp score, Dysphagia Outcome and Severity Scale score, Dysphagia Handicap Index score, and fNIRS data (optional) at baseline and at 3 months. Each of these data points will be entered into data files by participant number in LabTrack and Excel.

Paper case report forms will not contain any identifying information and will be stored in a locked cabinet at the James Madison University Neural Bases of Communication and Swallowing Laboratory, which requires authorized badge access. All deidentified data will also be recorded in the case report form on encrypted Laptops connected by VPN to the LabTrack system on a server in [name] laboratory. Participants' status at the end of each test session will be recorded in the CRF in LabTrack.

